## Scotopic perimetry in Age-related Macular Degeneration

[name]

Director, Rose-Silverthorne Retinal Degenerations Laboratory

Scientific Director, Retina Foundation of the Southwest

Director of Visual Electrophysiology and Adjunct Professor of Ophthalmology

University of Texas Southwestern Medical School

Perimetry is typically used for assessing the regional variations in function for patients with retinal disease. Standard perimetry only measures cone-mediated sensitivity. Until recently, it has not been possible to obtain rod-mediated perimetry other than by custom-built devices. There are many factors, however, that make rod-mediated fields attractive. Despite their different etiologies, retinal degenerations share many common features. For example, many of the mutations causing retinitis pigmentosa are expressed in rod photoreceptors, and night blindness is often the earliest symptom. Similarly, a growing body of evidence indicates that rods are affected early in age-related macular degeneration (AMD) and Stargardt disease. In addition, some of the contemporary treatment strategies are common to these diseases. These treatment strategies require localized outcome measures of rod and cone function to evaluate treatment efficacy.

The MP-1S was the first fundus perimeter to provide highly localized measures of rod and cone function. It incorporates a fundus-tracking system and follow-up mode to maintain constant stimulus projection on the retina and facilitate repeat testing of identical loci despite eye movements. The scotopic MAIA is a more recent option for scotopic perimetry. It provides a faster test, but has a limited dynamic range. Average normal sensitivity for elderly patients with spot size 3 within the macula is approximately 15 dB, so the machine has a floor effect for patients with losses  $> 1.5$  log unit. The MP-1S has a greater dynamic range because neutral density filters can be adjusted to fit the range needed for the patient. The mean normal value for 13 elderly subjects tested to date is 23 dB for a stimulus size 3. The 8 dB difference in normal scotopic sensitivity on the two fundus perimeters is also seen in patients with macular disease. To date, we have compared 10 patients on both devices. The correlation in mean sensitivity between the two devices is high ( $r = 0.73$ ) with the Nidek MP-1S having sensitivity on average 10 dB higher than the MAIA-2S.

The Nidek MP-3S is a next-generation fundus perimeter designed to replace the MP-1S. In general, it is easier to use than the MP-1S. It incorporates a red screen that does not interfere with the dark adaptation of the patient. Other advances include "fade-out-protection" for the fixation light to avoid the Troxler effect, which is particularly common in an otherwise dark field. Rather than the joystick on the MP-1S for aligning the patient, the MP-3S actively tracks the pupil position of the patient. Another important advantage of the MP-3S is the higher luminance of the background for standard testing. The 34 cd/m^2 background is 10 times brighter than the background of the MP-1, making it truly a photopic, rather than mesopic, test. Thus the MP-3S can be used in standard mode with a background that saturates rods and produces a cone-mediated sensitivity map, or in scotopic mode, with no background to produce a rod-mediated sensitivity field. Rather than having to insert filters as in the MP-1S, the filters in the MP-3S are fixed and

automatically moved into position when a scotopic test is specified. This leads to much greater ease of use and less possibility of technician error while running the test.

Representative normal sensitivity maps for 2 different spot sizes on the MP-3S are shown in Figure 1. For spot size 3, the values are comparable but slightly higher than for elderly subjects tested on the MP-1S (7 corresponds to 27 on the MP-1S, given the 2.0 log filter). For the larger spot size 5, values are considerably higher consistent with spatial summation. It is also important to point out that the range over which patients can be tested can be varied by adjusting spot size. There is a tradeoff between the greater spatial localization with spot size 3 and the larger dynamic range with spot size 5.

[figure not shown]

Figure 1. Comparison of spot sizes 3 and 5 on MP-3S in normal subject

In order to compare results from patients on the MP-3S to those from the MP-1S, we tested 10 patients with age-related macular degeneration using the following parameters:

Table 1 Comparison of Nidek MP-3S to Nidek MP-1S

[figure not shown]
	MP-3S	MP-1S
Mode	Scotopic	Scotopic
Pattern	NdkSctRed36p	AMD GA Rod Reduced
Test loci	32	32
Spot size	5	5
Filter	Internal	Blue+ 2.0
Fixation	3 deg circle	3 deg circle
Staircase	4:2	4:2

The patients will be greater than 55 years of age. Each patient will be evaluated with the following procedures:

- Best-corrected visual acuity of both eyes
- Slit lamp examination to screened for a narrow angle prior to dilation
- Pupil dilation with 30 minutes patching for dark-adapted testing of the better seeing eye
- Dark-adapted visual field test on Nidek microperimeter, model MP-3S using a protocol that takes approximately 20 minutes
- Dark-adapted visual field test on Nidek microperimeter, model MP-1S using a protocol that takes approximately 20 minutes
- Imaging on Heidelberg Spectralis Optical Coherence Tomography and fundus autofluorescence unit

MP-3S and MP-1S testing order will be randomized and both tests will be conducted on the same day. Coefficients of repeatability will be obtained for each test and compared to the literature. We will determine the range of values for point sensitivity to determine the amount that a patient has to change at a given location to be significant. The limits of agreement for the two devices measuring scotopic sensitivity will be compared to limits of agreement for mesopic testing.

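### Does the single MP-1S filter contradict the adjustable-range rationale and make the limits of agreement too narrow?

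*Protocol*

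**What the plan says.** All of this stands in the protocol's single narrative section, with Table 1 and the closing analysis paragraph.

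- **MAIA.** "Average normal sensitivity for elderly patients with spot size 3 within the macula is approximately 15 dB". From this figure the text infers a floor once loss exceeds 1.5 log units. The next statement is that "The MP-1S has a greater dynamic range because neutral density filters can be adjusted to fit the range needed for the patient".
- **MP-1S normal level.** "The mean normal value for 13 elderly subjects tested to date is 23 dB for a stimulus size 3".
- **MP-3S.** It is introduced as the successor to the MP-1S. The text notes that "the filters in the MP-3S are fixed and" switch in by themselves when a scotopic test is chosen. On the scales: "7 corresponds to 27 on the MP-1S, given the 2.0 log filter".
- **Spot size.** The text says that spot size also changes the testable range: "There is a tradeoff between the greater spatial localization with spot size 3 and the larger dynamic range with spot size 5".
- **Table 1.** Spot size 5 and 32 loci on both devices, an internal filter on the MP-3S, and a blue plus 2.0 filter on the MP-1S.
- **Analysis.** "The limits of agreement for the two devices measuring scotopic sensitivity will be compared" with those for mesopic testing. Coefficients of repeatability and a pointwise threshold for real change are also planned.

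The protocol states no lower limit for either device at these settings, no expected share of floored loci and no rule for handling them.

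**The concern.** The protocol criticises one device for its floor, credits the MP-1S with avoiding this through interchangeable filters, and then lists a single filter. Its own conversion puts the zero points of the two devices at the same level. A locus too damaged to register on either would then read the same on both and give a difference of exactly zero, which reflects absence of measurement and not agreement.

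If many such pairs entered as ordinary data, agreement could look best where neither device measures anything. The device offset would be pulled toward zero, and a change threshold built from such data could be too small for loci that can still be measured. The stated patient limits are AMD and age above 55; none concerns severity.

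**Working it through.** **1. The protocol's own decibel figures** (1 log unit = 10 dB)

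- Conversion: 7 + 2.0 × 10 = 27, as stated.
- MAIA: 15 dB / 10 = 1.5 log units, as stated.
- MP-1S minus MAIA normal: 23 − 15 = 8 dB, as stated.

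**2. Headroom at the Table 1 filter**

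Assume that both scales end at 0, which the protocol does not state. Zero on the MP-3S is then 27 − 7 = 20 dB on the MP-1S scale. At spot size 3 the elderly normal lies 23 − 20 = 3 dB above that. Table 1 uses spot size 5, whose gain is not given in the text. An assumed gain of 0 to 12 dB gives a headroom of 3 to 15 dB; 6 to 12 dB gives 9 to 15 dB.

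**3. Direction of the effect, in closed form**

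Let a share *p* of loci have difference exactly 0, and let the rest have mean *b* and SD *s*. The variance of all differences is (1 − p)s² + p(1 − p)b², so

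width ratio = √[(1 − p)(1 + p·b²/s²)].

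This is below 1 only if b² < s²/(1 − p). With assumed *s* = 4 dB:

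| p | b = 0 | b = 4 dB | b = 6 dB |
|---|---|---|---|
| 5% | 0.975 | 0.999 | 1.028 |
| 10% | 0.949 | 0.995 | 1.050 |
| 25% | 0.866 | 0.968 | 1.083 |
| 50% | 0.707 | 0.866 | 1.031 |

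**4. Simulation with loci floored on one or both devices**

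Assumptions: error SD 2 dB per device, between-locus SD 6 dB, both devices clipped at 0. The SD of an MP-1S reading is √(6² + 2²) = 6.32 dB, so mean levels of 6, 4, 2 and 0 dB put 17%, 26%, 38% and 50% of MP-1S readings at the floor. The ratio is observed SD of differences over uncensored SD.

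| MP-1S floored | no offset | 4 dB offset |
|---|---|---|
| 17% | 0.893 | 0.990 |
| 26% | 0.835 | 0.985 |
| 38% | 0.760 | 0.972 |
| 50% | 0.672 | 0.943 |

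The 4 dB is 27 − 23, the only offset the text hints at. With it, the distortion moves to the mean: at 26% floored, the observed mean difference is 3.30 dB instead of 4.

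**5. Sensitivity to headroom and floor alignment**

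Assumptions: error SD 2.8 dB per device, loss SD 6 dB. Ranges run from mean loss 5 dB to mean loss 10 dB.

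| Headroom | no offset | 4 dB offset |
|---|---|---|
| 3 dB | 0.54 to 0.32 | 0.75 to 0.53 |
| 9 dB | 0.82 to 0.62 | 0.92 to 0.80 |
| 15 dB | 0.96 to 0.85 | 0.98 to 0.94 |
| 20 dB | 0.99 to 0.96 | 1.00 to 0.98 |

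If the MP-3S floor lies 10 dB lower than the MP-1S floor (headroom 9 dB, mean loss 10 dB), the ratio is 1.12 with no offset and 1.21 with a 4 dB offset: the limits become too wide.

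**6. Would dropping doubly floored loci repair it?**

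Under the assumptions of step 4 with no offset and 26% floored, the ratio improves from 0.835 to 0.937. With a 4 dB offset it moves further from 1: 0.985 to 0.955 at 26%, and 0.943 to 0.915 at 50%.

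**The case for a change.** The strongest case for a change is this. Adjustability is the protocol's only explicit reason why the MP-1S should escape the floor, and the planned setting does not use it. Even a generous 12 dB gain from spot size 5 gives 15 dB of headroom, the same 1.5 log units that the protocol finds limiting in the MAIA. At 9 dB the narrowing could be material. Repeat tests on one device share a floor and should have almost no offset, so the no-offset results apply most directly to repeatability and the pointwise change threshold. Reporting floored loci would cost little.

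Part of this stands. Floored readings are possible, and an analyst who kept many of them as ordinary values could understate within-device variability. The rest does not carry a change:

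- The adjustable-filter sentence describes what the MP-1S can do relative to the MAIA. It makes no promise for this comparison. One MP-1S setting against a device with fixed filters is an ordinary design, since it holds conditions constant.
- The 3 dB headroom belongs to spot size 3, which Table 1 does not use. The better-seeing eye is tested, which may reduce the floored share.
- The 4 dB offset is itself weak: 27 converts a value from one normal subject's map in Figure 1, while 23 is a mean of 13 elderly subjects.
- Nothing in the protocol says that floored loci enter as ordinary values, or whether the limits are taken per locus or per patient mean.
- A censored mixed model fitted to about 10 patients rests on normality below the floor and is a debatable choice. The simpler repair can make matters worse (step 6).

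**Conclusion.** The concern does not call for a change. The background and Table 1 do not contradict each other, and the decibel figures reproduce. What remains is an unstated rule for floored readings, a detail commonly left to an analysis plan and one that a team already alert to floor effects on the MAIA can be expected to settle sensibly.

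The possible distortion runs from negligible (ratio 0.96 to 1.00 at 20 dB headroom) through substantial narrowing (0.62 at 9 dB headroom, mean loss 10 dB, no offset) to widening (1.21 with misaligned floors and a 4 dB offset). Where it falls depends on the device offset, the alignment of the two floors, the gain from spot size 5 and the share of floored loci. The first is only hinted at in the text and the other three are not given, so a flat statement that the limits will be too narrow is not supported. All ratios rest on the assumed error SDs, loss distributions and zero floors shown above.

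### Does leaving the balance and the analysis of test order unstated undermine the limits of agreement between the MP-3S and the MP-1S?

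*Protocol*

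**What the plan says.** All the relevant text is in the body of the Protocol, under its title heading. The procedure list has one patching step, "Pupil dilation with 30 minutes patching for dark-adapted testing of the better seeing eye", followed by one dark-adapted field test on each device, each "using a protocol that takes approximately 20 minutes". The closing paragraph adds "MP-3S and MP-1S testing order will be randomized and both tests will be conducted on the same day". It names the agreement output in one sentence: "The limits of agreement for the two devices measuring scotopic sensitivity will be compared to limits of agreement for mesopic testing".

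The protocol does not give the allocation method, the interval between the two tests, a formula for the limits, or the unit of analysis (single locus or patient mean). It also gives no SD of the device differences and no order effect. The number of patients appears only in the past tense, "we tested 10 patients with age-related macular degeneration using the following parameters", while the next description is in the future tense, "The patients will be greater than 55 years of age".

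**The concern.** There is one patching period of 30 minutes before two tests of about 20 minutes. If the tests run back to back, the second device meets an eye with about 20 more minutes in the dark, and a patient who may be more practised or more tired. Randomising the order makes the expected shift in the mean device difference zero. It does not take the order effect out of the spread of the differences: the effect enters as +d in patients tested in one order and as −d in the others. That spread sets the width of the limits of agreement, a named output that is to be compared with mesopic limits. Part of the width could then reflect test sequence and not disagreement between devices. A chance imbalance in a small sample would also move the observed offset.

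**Working it through.** The protocol states no figure to reproduce, so the check is conditional.

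**Inputs.** From the Protocol: randomised order, same day, 10 patients (if that is the study size). Assumed: d, the common effect of being tested second; σ, the within-order SD of the patient-mean difference; limits computed without an order term.

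**Model.** The difference MP-3S minus MP-1S equals δ + d if the MP-3S is second and δ − d if it is first, plus error with SD σ. With n₁ and n₂ patients per order:

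- shift of the unadjusted mean = d(n₁ − n₂)/n
- expected variance without an order term = σ² + d² × 4n₁n₂/[n(n − 1)]

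**Widening at 5:5, n = 10.** The multiplier of d² is 4 × 25/90 = 10/9, so the widening factor is √(1 + (10/9)d²/σ²).

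| d/σ | widening |
|---|---|
| 0 | 0% |
| 0.25 | 3.4% |
| 0.5 | 13% |
| 0.75 | 27% |
| 1 | 45% |

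In dB with σ = 3, the half-width 1.96√(9 + (10/9)d²) is 5.88 at d = 0, 6.23 at d = 1 (+6%), 7.19 at d = 2 (+22%) and 8.54 at d = 3 (+45%). With σ = 4 and d = 1 it is 8.11 against 7.84 (+3.4%).

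**Effect of balance.** The multiplier of d² is 1.11 at 5:5, 0.93 at 7:3 and 0.71 at 8:2. Balance therefore does not narrow limits computed without an order term; the added variance is largest at 5:5. Balance acts on the offset, which shifts by 0.4d at 7:3 and 0.6d at 8:2. If allocation were simple, 10 patients would split 7:3 or worse with probability 34.4% and 8:2 or worse with probability 10.9%. The expected shift is still zero. With σ = 3, the standard error of the offset is 3/√10 = 0.95 dB at 5:5. Under simple randomisation it is √[(9 + d²)/10], which is 1.00 dB at d = 1 and 1.14 dB at d = 2.

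**Effect of fitting order.** An order term returns the expected variance to σ² and costs one degree of freedom (8 instead of 9). Simulated root-mean-square error of the estimated SD (200,000 runs, n = 10, 5:5, σ = 3):

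| d (dB) | no order term | order fitted |
|---|---|---|
| 0 | 0.705 | 0.746 |
| 1 | 0.740 | 0.743 |
| 2 | 0.996 | 0.744 |
| 3 | 1.543 | 0.743 |

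Fitting is about 6% worse with no order effect (0.746/0.705 = 1.06), breaks even near d = σ/3, and is better above that.

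**Scale.** Even with no order effect, the SD estimate from 10 patients has an error of 0.705/3, about 23%. A widening of 6% or less is well inside that.

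**Unit.** The sentence before the one on agreement concerns point sensitivity at a given location, so the limits may be pointwise. The SD would then include locus-level noise and the same d would matter less. With an assumed σ of 6 dB and the large-sample factor √(1 + d²/σ²), the result is 1.014 at d = 1 and 1.05 at d = 2.

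**The case for a change.** The strongest argument for the concern is that allocation and the recording of start times are matters of conduct. They have to be settled before patients are tested, and a later analysis plan cannot recover them. By randomising order, the sponsor has also treated order as worth controlling, and one clause on blocking would cost almost nothing.

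Some of this stands. The variance argument is correct, a balanced list is good practice, and an order effect from longer dark adaptation, practice or fatigue is plausible.

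It does not make the protocol wrong. Silence on blocking does not mean the list is unblocked; that detail normally sits in the randomisation procedure. An unequal split also does little lasting damage. If the realised order is kept, fitting it removes the shift in the offset, and the simulated standard error of one limit is 0.593σ at 7:3 against 0.577σ at 5:5, about 3% more. Start times would help to explain an order effect, but the order term does not need them.

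The larger widening figures need a large d. Table 1 gives a 4:2 staircase for both devices. If those are step sizes in dB, d = 2 is a full smaller step averaged over all 32 loci, and nothing in the protocol suggests a shift of that size.

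**Conclusion.** The concern does not hold. The protocol randomises order, keeps both tests on one day and names limits of agreement without fixing how they are computed. Limits without an order term and an unbalanced list are both readings of its silence, on matters commonly left to a statistical analysis plan or a randomisation procedure. No statement, rule or conclusion in the document is shown to be wrong.

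The possible effect depends on four things the protocol does not give: back-to-back testing, an order effect, an SD, and the patient mean as the unit. The 5:5 figures also need 10 to be the study size. On those assumptions the widening is zero if d = 0, about 6% or less for d up to 1 dB with σ of 3 dB or more, and large only if d approaches σ.

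Fitting order is a legitimate choice, not a correction. It loses precision when d is below about σ/3 and gains above that, and d is unknown. If the mesopic limits carry no order term, a like-for-like comparison would still need the scotopic limits without one.

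### One test per device on a single day, with no second visit, cannot support the promised per-location criterion for change over time

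*Protocol*

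**What the plan says.** The list of procedures after Table 1 of the Protocol has one dilation with patching, then "Dark-adapted visual field test on Nidek microperimeter, model MP-3S using a protocol that takes approximately 20 minutes" and "Dark-adapted visual field test on Nidek microperimeter, model MP-1S using a protocol that takes approximately 20 minutes", then imaging. No item is repeated and no return visit is mentioned.

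The closing paragraph before the Appendix fixes the timing of the two devices: "MP-3S and MP-1S testing order will be randomized and both tests will be conducted on the same day". It goes on: "Coefficients of repeatability will be obtained for each test and compared to the literature". The next sentence says that the range of point sensitivities will be used to find "the amount that a patient has to change at a given location to be significant". No formula, significance level, standard deviation or interval between readings is attached to that threshold.

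The opening background gives the wider purpose of such measurements: "These treatment strategies require localized outcome measures of rod and cone function to evaluate treatment efficacy". The test pattern in Table 1 and the Appendix has 32 loci.

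**The concern.** A threshold for change in a patient at a location is a statement about two readings on one device, normally taken at different visits. Its error variance has two parts: the variation of repeated readings within a day, and the extra variation between days (adaptation, pupil, alignment, attention, fixation). A one-day schedule cannot show the second part. With one test per device, the first part is not observed either.

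An analysis plan may supply a formula that the protocol leaves open. It cannot estimate between-visit variance from patients seen once, so this is a mismatch between aim and design within the protocol itself. If the resulting figure were published as the amount of change that counts, a later treatment study could adopt it with an error rate nobody has measured.

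**Working it through.** The protocol states no threshold, variance or error rate, so there is no figure of its own to reproduce. The check is whether the described data contain what the aim needs, and what happens under each plausible construction of the threshold.

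**Inputs from the Protocol.** One reading per locus per device; both devices on one day; no second visit; 32 loci.

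**Assumptions (the Protocol gives no values).** Let s_w² be the variance of repeat readings on one device within a day, s_b² the added variance between visits, and k = s_b²/s_w², taken as 0, 0.25, 0.5 and 1. Let t² be the device-by-locus variance per device, with t²/s_w² from 0 to 1. Errors are normal, the nominal two-sided level is 5%, and s_w is the same on both devices.

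**Construction A: same-day repeats on one device (not listed in the Protocol).**

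- Same-day threshold: 1.96 × √2 × s_w = 2.77 s_w.
- Threshold needed across visits: 2.77 × √(s_w² + s_b²), which is larger by the factor √(1 + k).
- False-positive rate when the same-day threshold is used across visits: 2 × [1 − Φ(1.96/√(1 + k))].

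| k | √(1 + k) | Shortfall 1 − 1/√(1 + k) | False-positive rate per locus | Expected false flags in 32 loci |
|---|---|---|---|---|
| 0 | 1.00 | 0% | 5.0% | 1.6 |
| 0.25 | 1.12 | 11% | 8.0% | 2.5 |
| 0.5 | 1.22 | 18% | 11.0% | 3.5 |
| 1 | 1.41 | 29% | 16.6% | 5.3 |

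For scale, with an assumed s_w of 2 dB the same-day threshold is 2.77 × 2 = 5.5 dB; the across-visit threshold is 6.2, 6.8 or 7.8 dB for k = 0.25, 0.5 or 1.

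**Construction B: MP-3S minus MP-1S differences (the only paired readings listed).** Around the mean device difference, the half-width is 1.96 × √(2(s_w² + t²)). Its ratio to the across-visit threshold for one device is √[(1 + t²/s_w²)/(1 + k)].

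- t²/s_w² = 0 and k = 1: √(1/2) = 0.71, too small.
- t²/s_w² = 1 and k = 0: √(2/1) = 1.41, too large.
- t²/s_w² = k: 1.00, right by coincidence.

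**Construction C: the spread of point sensitivities across patients.** This reflects differences in disease between people, which is not the error of a repeat reading. It has no fixed relation to the across-visit threshold and may be larger or smaller.

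None of the three contains s_b². Only A has a known direction of error, and A needs readings that the Protocol does not schedule.

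**The case against.** The strongest reply is that the same-day sentence concerns the pair of devices. Same-day testing in random order is the right design for comparing them, and it does not say that repeat readings on one device would fall on that day. This stands: the same-day rule needs no change. It does not rescue the change criterion, because no other day is described.

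A reader might infer that the threshold will be too small and that stable patients will be flagged too often. The documents do not support that as a general statement. The Protocol gives no formula and schedules no same-day repeats on one device, and constructions B and C can err the other way.

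Three objections to the illustration also stand in part. The values of k are assumed, and at k = 0 there is no inflation. Table 1 specifies a 4:2 staircase; if this ends in 2 dB steps, readings are discrete and the normal-theory rates are approximate. Day effects shared across loci would move them together, so the counts in 32 loci are averages over patients and not what a typical patient would show.

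It can also be said that the treatment-efficacy sentence is general background and that this study has no treatment or follow-up. That is so, but the closing paragraph itself speaks of how much a patient has to change, so the aim does not depend on the background.

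Finally, the absence of any repeat on either device is the more basic gap. Filling it with a second test in the same session would still leave between-visit variance unobserved, so the present point needs its own correction.

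**Conclusion.** The point holds in this form: the described schedule cannot support a per-location criterion for change over time, because it has no visit-to-visit component and no within-device repeat. This rests on the Protocol's text alone.

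The size is conditional. If same-day repeats on one device were used, the threshold would fall short by 11% to 29% for k between 0.25 and 1, and the per-locus error rate would be 8% to 17% against a nominal 5%. If between-device differences were used, the threshold could be anywhere from 0.71 to 1.41 times the right value over the assumed ratios. The statement that it will be too small should not be made without that condition. The correction is worth making because it is nearly free and removes a claim the data cannot back.

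**What to change.** In the closing paragraph before the Appendix, replace the sentence on the per-location change threshold with:

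> We will estimate, at each location, the limits within which same-day MP-3S and MP-1S readings differ; these limits do not include visit-to-visit variability and will not be presented as a criterion for change at follow-up.

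If same-day repeats on one device are in fact done, the Protocol should say so. The within-device coefficient of repeatability may then be reported as same-day measurement error and as a lower bound for between-visit change. That label should not be applied to limits from between-device differences.

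The cost is a narrower claim; no visit or test is added. If the sponsor wants to keep a criterion for change at follow-up, the Protocol would have to state the number of repeats per device, their spacing (including separate visits) and the formula for the threshold, and that would mean additional testing.

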## Appendix

32-point pattern used for scotopic testing on MP-1S and MP-3S

Spot	X	Y
1	8	-4
2	4	-4
3	-4	-4
4	-8	4
5	-4	4
6	4	4
7	8	4
8	-4	-8
9	4	-8
10	4	8
11	-4	8
12	-8	-6
13	8	-6
14	8	6
15	-8	6
16	0	-10
17	-10	0
18	0	10
19	10	0
20	0	4
21	-4	0
22	0	-4
23	4	0
24	-8	-4
25	-6	-2
26	-6	2
27	-2	-6
28	2	-6
29	2	6
30	6	2
31	6	-2
32	-2	6

Coordinates for 32-point pattern

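### The protocol promises per-device repeatability coefficients and a pointwise change threshold, but lists one test per device and no retest, so neither can be estimated as written

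*Protocol*

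**What the plan says.** The procedure list in the protocol's main section applies to each patient. Three of its entries matter here:

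- The eye is prepared once: "Pupil dilation with 30 minutes patching for dark-adapted testing of the better seeing eye". No second preparation is listed.
- The newer device has a single entry, which reads "Dark-adapted visual field test on Nidek microperimeter, model MP-3S using a protocol that takes approximately 20 minutes". Nothing in it mentions a repeat.
- The older device likewise has a single entry, worded in the same way: "Dark-adapted visual field test on Nidek microperimeter, model MP-1S using a protocol that takes approximately 20 minutes". It mentions no repeat either.

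The paragraph after the list fixes the timing: "MP-3S and MP-1S testing order will be randomized and both tests will be conducted on the same day". It then states three analyses:

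1. Repeatability, for which the sentence is "Coefficients of repeatability will be obtained for each test and compared to the literature".
2. A pointwise change threshold. The spread of point sensitivities is to be used to "determine the amount that a patient has to change at a given location to be significant".
3. Limits of agreement between the two devices, compared with those for mesopic testing.

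The only patient number given for the MP-3S and MP-1S comparison is in the lead-in to Table 1: "we tested 10 patients with age-related macular degeneration using the following parameters". The Appendix gives the "32-point pattern used for scotopic testing on MP-1S and MP-3S". The only other mention of repeat testing is in the introduction, where it describes a feature of the MP-1S and not a study procedure.

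**The concern.** A coefficient of repeatability measures how far two results from the same patient on the same device differ when nothing has changed. It needs at least two runs per device per patient. So does a threshold for real change at one locus, if it is to come from this trial's data. The procedure list provides neither.

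The spread of sensitivities across patients and loci cannot stand in for a retest, because it mixes true differences with measurement error.

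As listed, two of the three analyses have no data behind them, and the planned comparison with published repeatability would have no matching figure from this trial. The introduction motivates the work by the need for localized outcome measures in treatment studies, so a change threshold is a result that later studies might reuse. A threshold built on the wrong variance could call noise a change, or miss a real one.

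**Working it through.** The protocol states no figure for this point, so there is nothing to reproduce. The question is whether the promised quantities can be estimated from the listed data.

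**Inputs.** Runs per device r = 1 (inferred from the procedure list). Loci per field = 32 (Table 1 and Appendix). Patients n = 10 (lead-in to Table 1, assumed to be the sample). The protocol gives no error SD, so every SD below is an assumption.

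**1. Degrees of freedom.** The coefficient is CoR = 1.96 × √2 × s, where s is the within-patient SD on one device. Its degrees of freedom are n × (r − 1).

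- As listed: 10 × (1 − 1) = 0, and 0 for any other n.
- Pointwise: 10 × 32 = 320 thresholds per device, with 0 replicate pairs.

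**2. Replicates within a run.** The Appendix lists 32 coordinates and all 32 are distinct, so no locus is listed twice.

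**3. Between-device differences as a substitute.** With one run each, the only within-patient contrast is MP-3S minus MP-1S. With independent errors, its variance is s₁² + s₂² + s_int², where s_int is the SD of the patient-by-device interaction. Four assumed settings (dB) give the same total:

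| s₁ | s₂ | s_int | Sum of variances | 1.96 × SD_diff | True CoR, device 1 / device 2 |
|---|---|---|---|---|---|
| 2 | 2 | 0 | 4 + 4 + 0 = 8 | 5.5 | 5.5 / 5.5 |
| 1.5 | 1.5 | 1.87 | 2.25 + 2.25 + 3.5 = 8 | 5.5 | 4.2 / 4.2 |
| 1 | 1 | 2.45 | 1 + 1 + 6 = 8 | 5.5 | 2.8 / 2.8 |
| 1 | 2.65 | 0 | 1 + 7 + 0 = 8 | 5.5 | 2.8 / 7.3 |

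One observed value is compatible with true coefficients from 2.8 to 7.3 dB. A simulation of 10 patients × 32 loci gave about 5.5 dB in all four settings.

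Taking each device's variance minus the between-device covariance does not solve this. It requires equal scales and independent errors, and even then it returns error plus interaction, not test-retest error.

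Same-day errors may also be correlated (ρ). Then 1.96 × SD_diff = 1.96 × √(2s²(1 − ρ) + s_int²):

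- s = 2.5, ρ = 0.5, s_int = 0: 4.90 against a CoR of 6.93, or 29% too low.
- s = 2.5, ρ = 0.5, s_int = 2: 6.28 against 6.93, or 9% too low.
- s = 1.5, ρ = 0, s_int = 0: 4.16 against 4.16, equal.
- s = 1.5, ρ = 0, s_int = 2: 5.71 against 4.16, or 37% too high.

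So the between-device figure is not even a bound on the coefficient.

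**4. Cross-sectional spread as a threshold.** With an assumed true SD of 5 dB, the simulated variance of point sensitivities in one test was about 26 to 32 dB² in these settings. Most of that is the true variance of 5² = 25 dB², so the spread says little about measurement error.

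**5. What a retest would give.** With r = 2, the 95% limits for the coefficient of mean sensitivity are √(df/χ²₀.₉₇₅) and √(df/χ²₀.₀₂₅) times the estimate:

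| n | df | Lower factor | Upper factor |
|---|---|---|---|
| 10 | 10 | 0.70 | 1.75 |
| 20 | 20 | 0.77 | 1.44 |
| 30 | 30 | 0.80 | 1.34 |

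**6. What one run does support.** At n = 10, each limit of agreement for mean sensitivity has a 95% half-width of t₉,₀.₉₇₅ × √(1/10 + 1.96²/(2 × 9)) = 2.262 × 0.560 = 1.27 SD_diff.

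**The case against.** The list names types of procedure without counts. On that view, the reference to two tests could mean two kinds of test, and the promise of repeatability is itself the sign that repeats were planned. The fault would then be an unstated number and timing of runs, and the natural cure would be to add the retest rather than withdraw the analyses. The change threshold might also rest on published values, since the sentence before it refers to the literature. The between-device comparison survives, and no treatment decision depends on the lost figures. The sample of 10 comes from a past-tense sentence, and the protocol never proposes 1.96 × SD_diff as a repeatability coefficient.

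Part of this stands. Single testing is inferred, a retest may have been intended, and a threshold from external data would be legitimate if labelled as such. The confidence factors depend on an assumed n, and the SD_diff illustration is peripheral: it only closes off a substitute.

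The core is untouched. Zero degrees of freedom needs no n. If a retest was intended, the procedure list is wrong instead, because it omits either same-day runs or a whole session. The threshold sentence names the spread of point sensitivities as its basis, not external retest data. An analysis plan, which was not available here, cannot create runs that no procedure collects.

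**Conclusion.** The concern holds. As listed, each device has 0 within-device degrees of freedom for any sample size, so no repeatability coefficient can be obtained. A threshold taken from the spread of point sensitivities would mix patient differences with measurement error. This affects two of the three stated analyses; the limits of agreement between devices remain sound. The conclusion rests on reading the list as one run per device, the only reading for which the document gives a schedule. The sample of 10 and all SDs are assumptions that affect only the illustrations.

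**What to change.** Reconcile the procedure list with the two analysis sentences.

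**Default, if no retest was intended.** Replace both sentences with wording such as: *Between-device bias and 95% limits of agreement (MP-3S minus MP-1S) will be reported for mean sensitivity and pointwise, with confidence intervals that allow for 32 loci per patient.* Drop the per-device coefficients and the comparison with published test-retest values. Drop the change threshold as well, or label it as taken from external test-retest data. Do not present 1.96 × SD_diff as a repeatability coefficient or as a bound on one. This costs wording only; the downside is that the trial gives up its own repeatability and change-threshold statements.

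**If a retest was intended.** Add it to the procedure list, state whether it falls on the same day or at a separate visit, and report the coefficient with its confidence interval. On the protocol's own times the listed dark-adapted session is 30 + 20 + 20 = 70 minutes. A same-day retest of both devices adds 20 + 20 = 40, making about 110 minutes. A separate visit adds about 70 minutes and a second dilation.
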